14.0 ADVERSE EVENTS

14.1 Adverse Events (AE)

Adverse Event (AE): any untoward medical occurrence in a patient or clinical study subject.

Serious Adverse Event (SAE): any untoward and unexpected medical occurrence or effect that:

- Results in death
- Is life-threatening refers to an event in which the subject was at risk of death at the time of the event; it does not refer to an event which hypothetically might have caused death if it were more severe
- Requires hospitalisation, or prolongation of existing inpatients' hospitalisation
- Results in persistent or significant disability or incapacity
- Is a congenital anomaly or birth defect

Medical judgement should be exercised in deciding whether an AE is serious in other situations. Important AEs that are not immediately life-threatening or do not result in death or hospitalisation but may jeopardise the subject or may require intervention to prevent one of the other outcomes listed in the definition above, should also be considered serious.

14.2 Reporting Procedures

All adverse events should be reported. Depending on the nature of the event the reporting procedures below should be followed. Any questions concerning adverse event reporting should be directed to the Chief Investigator in the first instance.

14.2.1 Non serious AEs

All such events, whether expected or not, should be recorded.

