5.7 Follow-up

Two months after randomisation, parents will be contacted by the researcher to make arrangements for the first follow-up assessment. Follow-up assessments will take place at a time which is convenient for the parent and their child. A final follow-up interview will be conducted 12 months after randomisation.

Follow-up interviews will be carried out through face-to-face interviews. Any travel costs or other reasonable expenses incurred by the parents will be reimbursed. In addition to these assessments, all study participants will be contacted nine months after randomisation using their preferred method (text, email, letter, phone call), to thank them for their participation, to remind them of the plan for their final follow-up interview and to ask them to let us know of any changes in their contact details.

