6.2 Treatment intensity

The TIME-A trial involves two active treatment groups in which music therapy sessions are delivered at two different levels of intensity; once a week (low intensity) or three times a week (high intensity). Over the five month treatment period, those in the low intensity treatment arm will receive up to 20 sessions of music therapy and those in the high intensity treatment arm will receive up to 60 sessions. Previous trials of improvisational music therapy based on both high and low intensity treatment have reported positive effects [4,5]. Low intensity treatment is less costly to deliver and requires less commitment from children and their parents, but some therapists argue that treatment delivered more frequently has a greater impact on a child's communication skills and functioning.

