6.3 Enhanced treatment as usual

All parents of study participants will receive enhanced treatment as usual; in addition to usual care from primary and secondary services, parents will receive three counselling sessions delivered over a five month period (at baseline, two months and five months). These sessions will be delivered by experienced clinicians who receive regular supervision and comprise psychoeducation, information about support organisations and support in coping with current problems. This type of support is recommended for parents of children with ASD [7], and will help ensure that all study participants receive a basic level of support across all study centres.

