6.4 Treatment fidelity

To determine whether treatment is delivered as intended, therapists will document significant events, notable child behaviours and interventions used after every session. In addition to these self-reports all music therapy and parent counselling sessions will be video-taped to allow for assessment by independent raters. Notes and video-recordings will be used during monthly supervision sessions and video-recordings will be monitored by the lead music therapist in the study. The video recordings shall only be stored for 1 year after the study's results have been published.

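### All adverse events are to be recorded, but no enquiry common to the three arms is fixed, and staff contact during treatment differs so much by arm that any harm summary is at risk of ascertainment bias

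*Protocol*

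**What the plan says.** **The rule.** Protocol section 14.2 states: "All adverse events should be reported". Section 14.2.1 adds for non-serious events: "All such events, whether expected or not, should be recorded". Section 14 defines adverse and serious adverse events and gives reporting routes. It names no person who asks, no time of asking and no question.

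**Shared visits.** Sections 12.0 to 12.2 place data collection before randomisation and at 2, 5 and 12 months. The items listed are eligibility, demographic, cognitive and outcome measures; none concerns adverse events. Under section 5.7 all families are also contacted at nine months, "to thank them for their participation, to remind them of the plan for their final follow-up interview", and to learn of changed contact details.

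**Contacts in all arms.** Section 6.3 gives every family three parent counselling sessions, at baseline, two months and five months.

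**Contacts on music therapy only.** Section 6.2: "those in the low intensity treatment arm will receive up to 20 sessions of music therapy"; the high-intensity maximum is 60. Section 6.4: "therapists will document significant events, notable child behaviours and interventions used after every session". The same section says that "all music therapy and parent counselling sessions will be video-taped to allow for assessment by independent raters", so counselling, which controls also receive, is recorded on video.

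**Knowledge of allocation.** Under section 5.6 the trial coordinator, parents and therapists learn the allocation, while the researchers who assess outcomes are to stay masked.

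**The concern.** An instruction to record everything, without a prompt, yields the events that staff happen to see or be told about. The yield depends on how often staff meet the family, and here that frequency is part of the randomised treatment. If the true event rates were equal, the music therapy arms would probably still show more recorded events, because a therapist sees the child weekly or three times a week and writes a note each time.

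At stake is the credibility of any harm table by arm, including tables for the data monitoring and ethics committee mentioned in section 13.0. An analysis plan cannot repair this: events in controls that nobody asked about are not in the data.

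A second, smaller matter is timing. After month 5 the next scheduled contacts are at months 9 and 12, and neither is stated to include a question about events. This gap is the same in every arm, so it bears on timely awareness of serious events and not on bias between arms.

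**Working it through.** The protocol gives no adverse-event rate and no harm comparison, so there is no figure to reproduce. The check counts scheduled contacts and then shows what unequal recording could do under stated assumptions.

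**1. Scheduled contacts** (sections 5.7, 6.2, 6.3, 12.0, 12.2; session numbers are maxima)

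| Counting rule | Control | Low | High | Low/control | High/control |
|---|---|---|---|---|---|
| Treatment months, post-baseline time points (2 and 5 months; counselling and assessment coincide) | 2 | 22 | 62 | 11 | 31 |
| Treatment months, two assessments and three counselling sessions counted separately | 5 | 25 | 65 | 5.0 | 13 |
| 12 months, three follow-up assessments | 3 | 23 | 63 | 7.7 | 21 |
| 12 months, plus three counselling sessions | 6 | 26 | 66 | 4.3 | 11 |
| 12 months, plus nine-month contact | 7 | 27 | 67 | 3.9 | 9.6 |

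Over the full 12 months the ratio lies between about 4 and 21, depending on the count and the intensity. Section 7.0 lists only five and 12 months as follow-up times, against 2, 5 and 12 in sections 12.0 and 12.2. Those passages need reconciling; the counts above use section 12.

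**2. Capture under a recall window** (assumption: an event is recorded only if a contact follows within w weeks; all sessions take place, and every contact brings the event to light)

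Treatment period T = 5 × 52/12 = 21.7 weeks. Capture is about 2w/T in controls and about min(1, 20w/T) at low intensity.

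- w = 1: control 2/21.7 = 9%; low intensity 20/21.7 = 92%; ratio about 10.
- w = 4: control 8/21.7 = 37%; low intensity about 100%; ratio 2.7.
- Full recall between visits: both about 100%; ratio 1.

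In this model high intensity captures about 100%, so high against low differs by at most 1/0.92 = 1.09. The contrast that matters is music therapy against control.

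**3. Effect on a table of children with any event** (assumption: equal true risk; recording probabilities are illustrative)

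The 2:1:1 allocation of 300 gives 150 control against 150 music therapy. Expected number recorded = n × true risk × recording probability. With recorded proportions p1 and p2, the chance of a nominally significant excess at two-sided 5% is Φ((p2 − p1 − 1.96·SE0)/SE1), where SE0 is the pooled and SE1 the unpooled standard error.

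True risk 30%:

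- Recording 50% v 70%: 150 × 0.30 × 0.50 = 22.5 against 150 × 0.30 × 0.70 = 31.5; ratio 1.40; chance about 27%.
- Recording 50% v 90%: 22.5 against 40.5; ratio 1.80; chance about 73%.
- Recording 80% v 90%: 36 against 40.5; ratio 1.13; chance about 9%.

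With a true risk of 10% the ratios are unchanged and the chances are about 11%, 27% and 5%. For the UK sample alone (50 v 50, true risk 30%) they are about 12%, 31% and 5%. With equal recording the ratio is 1.0.

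**The case against.** The strongest reply is that no between-arm comparison of adverse events is planned. Safety is not among the objectives, hypotheses or outcomes, and section 14 deals with recording and expedited reporting. The therapists' notes belong to treatment fidelity and supervision, and nothing makes them a source for the adverse-event record. Question wording and forms often sit in a case report form or safety procedure that is not shown here.

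Much of this stands, and it limits the point to a risk of bias. It does not remove it. Under a rule that every event be recorded, a therapist who sees or hears of one should report it, whatever use is made of the session notes. Any later summary by arm would inherit the imbalance.

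Four stronger readings are tempting, and the documents do not support them:

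- That controls are seen only twice. This is true of post-baseline time points during treatment, but not of the trial, which adds a 12-month assessment and a nine-month contact.
- That music therapy children receive 20 or 60 sessions. These are maxima.
- That harm counts are inflated about tenfold. That figure needs one-week recall, full attendance and complete elicitation at each session, none of which the protocol states.
- That the gap after month 5 defeats the 24-hour report of serious events. Section 14.2.2 gives no start point for the 24 hours, and its 15-day limit runs from the Chief Investigator's awareness.

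**Conclusion.** The point holds as a weakness in data collection that should be corrected. The protocol asks for complete recording of adverse events but fixes no enquiry common to the arms, and its design gives the music therapy arms many times the control arm's scheduled contact during treatment. Any harm summary by arm is at risk of ascertainment bias, most likely against music therapy.

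The size cannot be determined from the protocol. It depends on parents' recall at the shared visits and on whether therapists report what they see and hear. The range runs from no distortion with full recall to a several-fold spurious ratio if short-lived events are forgotten between contacts. The recording probabilities and risks used in the illustrations are assumptions.

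The absence of a stated enquiry between months 5 and 12 is a separate matter, equal in all arms. Its consequence is possible delay in learning of a serious event.

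**What to change.** - In sections 12.0 and 14.2, add one short parent-completed event form (new illness, injury, hospital contact, marked distress or change in behaviour), identical in all three arms, at the existing 2-, 5- and 12-month visits.
- Have it returned to the trial coordinator, who already knows the allocation, so that the outcome assessors stay masked.
- Add a question on hospital contact to the existing nine-month contact.
- State that any between-arm harm summary rests on these commonly timed reports, and list events known only from therapy sessions separately.

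The cost is a small amendment, one page at visits that already take place, a few minutes for parents and slightly more events to process. Parents know the allocation, so some reporting bias would remain; the form equalises the opportunity to report, not the inclination.

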14.2.2 Serious AEs

An SAE form should be completed and faxed to the Chief Investigator within 24 hours. However, hospitalisations for elective treatment of a pre-existing condition do not need reporting as SAEs.

All SAEs shall be reported to the [Insert REC Name] and sponsor where in the opinion of the Chief Investigator, the event was:

- 'related', i.e. resulted from the administration of any of the research procedures; and
- 'unexpected', i.e. an event that is not listed in the protocol as an expected occurrence

Local investigators should report any SAEs as required by their Local Research Ethics Committee, Sponsor and/or Research & Development Office.

Reports of related and unexpected SAEs shall be submitted within 15 days of the Chief Investigator becoming aware of the event, using the NRES SAE form for non-IMP studies.

Local investigators should use the following contact details when reporting any SAEs:

Please Fax SAE forms to: [name] – FAO: Trial Coordinating Office

15.0 REGULATORY ISSUES

15.1 Ethics Approval

The Chief Investigator has obtained approval from the [Insert REC Name] Research Ethics Committee. The study must be submitted for Site Specific Assessment (SSA) at each participating NHS Trust. The Chief Investigator will require a copy of the Trust R&D approval letter before accepting participants into the study. The study will be conducted in accordance with the recommendations for physicians involved in research on human subjects adopted by the 18th World Medical Assembly, Helsinki 1964 and later revisions.

15.2 Consent

Consent to enter the study must be sought from each participant only after a full explanation has been given, an information leaflet offered and time allowed for consideration. Signed participant consent should be obtained. The right of the participant to refuse to participate without giving reasons must be respected. After the participant has entered the study the clinician remains free to give alternative treatment to that specified in the protocol at any stage if he/she feels it is in the participants remain within the study for the purposes of follow-up and data analysis. All participants are free to withdraw at any time from the protocol treatment without giving reasons and without prejudicing further treatment.

15.3 Confidentiality

The Chief Investigator will preserve the confidentiality of participants taking part in the study and is registered under the Data Protection Act.

15.4 Indemnity

Imperial College London holds negligent harm and non-negligent harm insurance policies which apply to this study.

15.5 Sponsor

Imperial College London will act as the main Sponsor for this study. Delegated responsibilities will be assigned to the NHS trusts taking part in this study.

15.6 Funder

TIME-UK is funded by the NIHR Health Technology Assessment programme.

15.7 Audits

The study may be subject to inspection and audit by Imperial College London under their remit as sponsor and other regulatory bodies to ensure adherence to GCP and the NHS Research Governance Framework for Health and Social Care (2nd edition).

16.0 DISSEMINATION AND PROJECTED OUTPUTS

The main output from this study will be high quality evidence on the clinical effectiveness of music therapy for children with autism spectrum disorders. By including data from up to 100 children who are using NHS services we will ensure that the findings of the main TIME-A trial are generalisable to the UK. Findings from the TIME-A trial will be used by the National Institute for Health and Clinical Excellence and other bodies when they develop future guidelines for the treatment of children with this condition. Information about the clinical effectiveness of this treatment approach will also be of considerable value to providers of NHS services and help inform choices about investment in music therapy and other psychosocial interventions which are provided in the NHS. Finally data on the impact of music therapy for children with ASD will be of value to parents and guardians of children with ASD as they will be able to make better choices about the interventions and treatments for their child(ren).

16.1 Dissemination of the results of the main trial

The project outputs from the main trial will be co-ordinated by the main trial centre in Norway. This will include: written reports on trial findings and presentations and workshops at a national and international meetings. The consortium of centres participating in the main trial includes teams from North America, Europe, Australasia and East Asia. The international makeup of the team will help ensure that results of the main trial are disseminated internationally and have the potential to have a global impact.

Plans for disseminating the results of the main trial include publishing papers in peer reviewed journals. In addition to the main paper, which will focus on the main study outcomes, papers on the process of delivering improvisational music therapy to children with ASD and papers examining the impact of the intervention in sub-groups of patients will also be published. Study findings will be presented at international conferences including the annual Autism-Europe International Congress and the International Centre for Research into Arts Therapies.

16.2 Dissemination of the results of the UK-arm of the trial

We will prepare a full report to NIHR: HTA that will detail the results of the UK arm of the TIME-A trial and place these in the context of findings from the international study. These findings will provide the basis for a paper on the process and outcomes of the UK arm of the TIME-A study. We will also prepare an English version of the treatment guidelines for improvisational music therapy as used in the main study which will be made freely available to all those working in the NHS.

We will present findings from the UK arm of the trial in the context of the international study at local and national meetings. At a local level we will convene a seminar open to the study team and participants to discuss study findings. At a national level we will present the findings of the study at the National Autistic Society's professional conference and the annual meeting of the British Association of Music Therapists.

16.3 Dissemination to parents of children with ASD

Each parent/ guardian who takes part in the study will be sent a personal letter thanking them for their involvement in the study. This will also include a short summary of the study findings both from the UK arm of the study and the international trial. This will include details of how parents can obtain further information about the project. This summary will be prepared with input from our Project Advisory Group. The group will also help us prepare a lay summary of project findings that will be made available on the internet through the web site of the Mental Health Research Network, and dedicated web pages at Imperial College London.

17.0 PLAN OF INVESTIGATION AND TIMETABLE

Milestones	Timelines	
Start date for project	1 st June 2014	
Funded set-up phase		
Appoint trial manager and local researchers	June 2014	
Publicise study among local clinicians	June 2014 onwards	
Train local researchers	June-August 2014	
Induct local investigators	June-August 2014	
Recruitment and follow-up		
Start participant recruitment	1 st September 2014	
First follow-up interview	1 st November 2014	
Complete recruitment	31 st August 2015	
Complete follow-up	31 st August 2016	
Analysis and write-up		
Analyze data	September to November 2016	
Submit final project report	30 th November 2016	

17.1 Project milestones

18.0 PROJECT MANAGEMENT

The Chief Investigator ([name]) will have overall responsibility for the research. He will be accountable for achieving project objectives and milestones, and ensure that the research is run in accordance with agreed procedures and protocols. He will direct the Operational Research Team which meet monthly and will consist of [name], [name], and [name]. The purpose will be to review progress and address issues of

implementation. [name] with have responsibility for supervising the local researcher, overseeing recruitment and follow-up of study participants in Cambridge and Essex. [name] will hold these responsibilities for London sites.

A Project Management Group (PMG), chaired by [name] and consisting of co-applicants, will meet on eight occasions over the course of the study. Its purpose will be to oversee the smooth running of the trial, monitor project achievements and weaknesses, review emergent findings at each research phase, and formulate actions required to address significant issues related to project progress.

19.0 APPROVAL BY ETHICS COMMITTEE

Multi-Centre Research Ethics Committee approval will be obtained prior to the start of data collection. Only children whose parent or guardian agrees to provide written informed consent will be included in the study. The parent of each potential participant will be provided with a copy of a Patient Information Sheet that includes a contact number for the study team. The trial will be conducted in accordance with Good Clinical Practice guidelines.

Risks and benefits for trial participants

Each study participant will have the same chance of being allocated to the three trial arms and all parents will be offered the three parent counseling sessions. By taking part in this trial participants and their families will be helping us find out whether music therapy helps children with Autism Spectrum Disorder. If music therapy is effective, this is likely to change the way that children with ASD are treated in the future. If it is not, then the results of the study will help to ensure that fewer children are given ineffective treatments in the future.

Study participants will be asked to give up their time to take part in study interviews and to complete study questionnaires. Baseline assessment takes no longer than 60 minutes observing children and no longer than 120 minutes with parents. Follow-up assessments will require no more than 90 minutes with children and 120 minutes with parents. All parents/ guardians will be offered a £20 honoraria following completion of the 12-month follow-up interview.

As we will collect information on a range of sensitive personal matters such as mental health and behavior we ensure that data is collected and stored carefully. Baseline data will be entered onto a web-based Case Report Form that will not include the patient's name or other information that could identify them. All data will be stored on a secure dedicated web server (based in Norway). Access will be restricted by user identifiers and passwords (encrypted using a one way encryption method). All electronic databases will use a patient identification number rather than the participant's name. Hard copies of data sheets linking the patient identification number to the person's contact details will be kept securely in a locked filing cabinet in a locked office at each participating site, and will only be accessible to a small number of people who are involved in the study.

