2.0 SUMMARY OF RESEARCH

TIME-A is a multi-centre international study of music therapy for children with Autism Spectrum Disorder (ASD) that has been funded by the Research Council of Norway. The international study is a three-arm, parallel group, researcher-blind, randomised trial testing the impact of music therapy plus enhanced treatment as usual versus enhanced treatment as usual alone over a 12 month period. Study participants are children aged from 4:0 to 6:11 years old, who have a clinical diagnosis of ASD, confirmed by independent assessment using validated diagnostic tools (the Autism Diagnostic Observation Schedule [1] and the Autism Diagnostic Interview-Revised [2]). Children who are already receiving music therapy or have done in the past will be excluded from the study, as will children with severe sensory impairment.

Study participants in the UK arm of the trial, which shall be funded by the NIHR HTA, will be recruited from NHS health services at six centres: Cambridge, Essex, Peterborough, and the London Boroughs of Hillingdon, Kensington & Chelsea and Westminster.

In keeping with the international study we will examine the impact of improvisational music therapy. This approach to delivering music therapy was originally developed in the UK [3]. It is the approach that is most widely used to deliver music therapy to children with autism in the NHS and has demonstrated efficacy in small scale trials [4,5]. All those in the trial will also receive enhanced treatment as usual: in addition to usual input from primary and secondary care, parents/ guardians will receive three counselling sessions delivered over a five month period. These sessions will be delivered by experienced clinicians who receive regular supervision and comprise psychoeducation, information about support organisations and support in coping with current problems in keeping with national guidelines [7]. In addition to this, those in one of the two active treatment arms of the trial will be offered either: low-intensity music therapy (weekly sessions for five months), or high-intensity music therapy (sessions three times a week for five months).

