5.6 Randomisation

Researchers at each site will enter the results of the baseline assessment on a web-based Case Report Form. Remote web-based randomisation will be undertaken through a fully automated service operated by Uni Research (Norway). The allocation ratio for the study is 2:1:1 such that equal numbers of participants are allocated to enhanced treatment as usual and music therapy and, among those allocated to music therapy, equal numbers will be allocated to high and low-intensity treatment. Randomisation will be made in blocks, with block size randomly assigned to between four and eight. Following randomisation the UK-based trial coordinator will be informed which arm of the trial the participant has been assigned to. Parents and therapists will then be given information about allocation status and arrangements made for delivering parent counselling sessions. For those in one of the two active arms of the trial, arrangements will also be made for delivering music therapy sessions. Study researchers are based in separate departments to those involved in organising treatment, helping to ensure they remain masked to the allocation status of study participants.

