11.3 Sample size calculation for the main trial

A total sample of 300 needs to be recruited in the study as a whole. Previous trials of improvisational music therapy for children with ASD have reported medium effect sizes associated with active intervention. A Cochrane review of music therapy for children with ASD calculated a Standardised Mean Difference of 0.50 for gestural communication skills and 0.36 for verbal communication skills [6].

A sample of 235 patients will provide 90% power to detect a medium effect size of the intervention on the social communication scale of the ADOS score at 12 months with a 5% level of statistical significance [32]. To take account of possible clustering at the level of study therapists and study centres and a drop out we have inflated the total sample required to 300. Loss to follow-up in trials of psychosocial intervention for children with autism spectrum disorder tends to be low. The PACT trial of parent mediated communication focused treatment reported a follow-up rate of 96% at 13 months [11].

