11.4 Sample size for the UK arm of the study

To achieve a total sample of 300 participants in the main trial, it has been calculated that 100 participants will need to be recruited in the UK. This sample will also be large enough to provide valuable information about the clinical effectiveness of delivering this intervention in the NHS.

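### The risk-benefit text in section 19 describes three equally likely arms, but section 5.6 allocates 2:1:1, so it misdescribes a family's chance of music therapy

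*Protocol*

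**What the plan says.** Two places in the Protocol describe how likely each arm is.

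- Section 5.6 (Randomisation) gives the ratio and explains it: "The allocation ratio for the study is 2:1:1 such that equal numbers of participants are allocated to enhanced treatment as usual and music therapy". It then says that "among those allocated to music therapy, equal numbers will be allocated to high and low-intensity treatment".
- Section 19.0, in its text on risks and benefits, says: "Each study participant will have the same chance of being allocated to the three trial arms". The same sentence adds that every parent is offered the counselling sessions.

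Section 2.0 confirms that two of the three arms receive music therapy, one at low and one at high intensity. No section gives a numerical chance of receiving music therapy.

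On blocking, section 5.6 says: "Randomisation will be made in blocks, with block size randomly assigned to between four and eight". It does not list the permitted sizes.

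**The concern.** The two descriptions of allocation do not agree. A 2:1:1 ratio makes one arm twice as likely as either of the others, whereas the same chance for three arms means thirds.

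The chance of receiving the treatment under test is something an ethics committee weighs and parents need when they decide whether to take part. Under section 5.5 parents decide with the Patient Information Sheet in hand, and section 20.2 shows that this sheet was still to be designed. If its text were drawn from section 19, the error could reach families.

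The block-size wording is a separate and smaller matter. It sets a range without saying which whole numbers in that range may be used, and not all of them are compatible with 2:1:1.

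**Working it through.** **Inputs.** Ratio 2:1:1, with the larger share to enhanced treatment as usual alone (section 5.6). Three arms, two of them music therapy (section 2.0). UK sample 100 (section 11.4). Total sample 300 (section 11.3). Block size from four to eight (section 5.6).

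**Step 1: does section 5.6 agree with itself?** The chance of an arm is its part of the ratio divided by the sum of the parts, 2 + 1 + 1 = 4.

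- Enhanced treatment as usual alone: 2/4 = 50%
- Low intensity: 1/4 = 25%
- High intensity: 1/4 = 25%
- Any music therapy: 1/4 + 1/4 = 50%

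This matches the section's own explanation: equal shares to usual care and music therapy, then equal shares by intensity.

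**Step 2: what section 19 implies.** With the same chance for each of three arms, each has 1/3 = 33.3%. Any music therapy is then 1/3 + 1/3 = 66.7%.

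**Step 3: the difference.**

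| | Section 5.6 | Section 19, plain reading |
|---|---|---|
| Chance of usual care alone | 50% | 33.3% |
| Chance of any music therapy | 50% | 66.7% |
| UK sample of 100: usual care / low / high | 50 / 25 / 25 | about 33 each |
| UK sample of 100: on music therapy | 50 | about 67 |
| Total of 300: usual care / low / high | 150 / 75 / 75 | 100 each |
| Total of 300: on music therapy | 150 | 200 |

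The chance of music therapy is overstated by 66.7 − 50 = 16.7 percentage points, and the chance of usual care alone is understated by the same amount.

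**Step 4: block sizes.** A block of size b holds 2:1:1 exactly only if b/2 and b/4 are both whole numbers, so b must be a multiple of 4.

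| b | b/2 | b/4 | b/4 | Holds 2:1:1 |
|---|---|---|---|---|
| 4 | 2 | 1 | 1 | yes |
| 5 | 2.5 | 1.25 | 1.25 | no |
| 6 | 3 | 1.5 | 1.5 | no |
| 7 | 3.5 | 1.75 | 1.75 | no |
| 8 | 4 | 2 | 2 | yes |

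A block of 6 can still split usual care and music therapy equally (3 and 3), but it cannot divide the 3 music therapy places equally by intensity.

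**The case against.** **The sentence may mean something else.** Its subject is each participant, and its second half concerns what all parents are offered. It could mean that every family faces the same set of chances as every other family, which is true under 2:1:1. That reading is possible but not the natural one, because the words compare chances across the arms. A risk-benefit statement that can reasonably be taken as one third each still needs rewording. What stands of the objection is that the 2/3 figure is implied; the Protocol does not state it.

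**Section 5.6 is the operative text.** It is explicit and explains its ratio, and anyone reading the whole Protocol would find it. This stands. Nothing in section 19 alters how children are allocated, the comparison made, the analysis or the sample size.

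**A reader might infer that parents are misinformed, and that control families would therefore drop out or seek music therapy elsewhere.** The documents do not support this. The information sheet has not been seen, nothing shows that it repeats section 19, and the Protocol gives no evidence linking expectations to drop-out.

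**A reader might infer that the block sizes are incompatible with 2:1:1, or that they would upset the overall split.** That goes too far. The two sizes actually named, four and eight, hold the ratio exactly. The text does not say that 5, 6 or 7 are used, and the settings of the automated system are not shown. Even if such sizes were used, imbalance within a block would not by itself prevent 2:1:1 overall. Only the imprecise wording remains.

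**Conclusion.** The contradiction is real and should be corrected. On its plain reading, section 19 implies a 2/3 chance of music therapy where section 5.6 gives 1/2, a difference of 16.7 percentage points, or about 17 children in the UK sample of 100. This rests on two assumptions: that the section 19 sentence compares the arms with one another, and that section 5.6, which explains its ratio in words, is the intended allocation.

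It is an error of description in a consent-relevant place. It is not a fault in the design or the analysis, and the importance is moderate. The block-size wording is a secondary clarification: 4 and 8 work, 5 to 7 do not hold the ratio exactly, and the text leaves open which are used.

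**What to change.** 1. **Section 19.** Replace the sentence with one saying that each child has a 1 in 2 chance of enhanced treatment as usual alone, a 1 in 4 chance of added low-intensity music therapy and a 1 in 4 chance of added high-intensity music therapy. Keep the statement that all parents are offered the counselling sessions.
2. **Patient Information Sheet.** Check that any chances it gives are these figures, and correct it if they are not.
3. **Section 5.6.** State that blocks are of size 4 or 8, in random order, after confirming this against the settings of the randomisation system.

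The cost is one sentence in section 19, a few words in section 5.6 and two checks. Sample size, allocation ratio and analysis stay as they are.
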